TITLE PAGE

New Therapeutical Perspectives in Cases of Phonological
Disorders

28053914.1.0000.5346

DOCUMENT DATE: 20/11/2018

STUDY PROTOCOL WITH SAP- STATISTICAL ANALYSIS PLAN

Objectives: The objective of this research was to analyze and compare phonological aspects such as phonetic inventory, phonological system, severity of the speech sound disorders, altered distinctive traits and phonological processes, as well as phonological and phonoarticulatory awareness, besides the auditory aspects of the abilities and variables present in Long Auditory Evoked Potential Long. Comparisons of the phonological and auditory aspects were performed before and after the intensive period of treatment in children with speech sound disorders. Twenty-five therapy sessions were assigned. The children were randomly drawn among three groups. Group 1 - Placebo: This group received no specific treatment for speech deviations, only used the computer resource to play on a website. The Group 2-Cycles Traditional: the therapy used the Modified Cycles Model. And the Group 3-SIFALA ("Speech Intervention Software"): the therapy used the proposal of the Strata Model based on Stimulability and Segment Complexity that was developed in software format. The categorization of these groups obeys the methodological questions of a randomized clinical trial. The evaluation of the children and the treatment of one of the SIFALA group were carried out by the responsible researcher. The other two groups were treated by fellowship academics of the Speech Language Pathology program. The reassessment of all procedures was performed by speech language pathologists with experience in speech and hearing areas who did not have knowledge about the variables of the research, so it was categorized as a single-blind trial. After the treatment period, the data were compared by means of the statistical analysis that used as a criterion to estimate the effects in each therapy group using the linear regression model with mixed effects for the quantitative variables responses. Also

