was used the polytomous logistic model for ordinal qualitative variables. In addition, Chi-Square and Wilcoxon tests were used for analysis of the abilities and variables of Long Auditory Evoked Potential. A significance level of 0.05 was set for all tests. Most of the children treated presented gains in the phonological and auditory variables. The therapeutic models used fulfilled the objective of reorganization of the phonological system, being possible to point out as innovative and differentiated the model using *software*-SIFALA. Key Words: Children. Language. Speech Sound Disorders. Auditory Perception. Rehabilitation of Speech Sound Disorders.

STATISTICAL ANALYSIS PLAN

The variables chosen for the static analyzes characterize the phonological and auditory aspects of the evaluations applied before and after the treatment period. For the phonological aspects, we adopted the variables that determine the phonological system, dividing sounds by the following criteria: acquired, partially acquired and not acquired; (SHRIBERG et al., 1997), altered distinctive traits and phonological processes. The PCFO (SEABRA and CAPOVILLA, 2012) and the evaluation of phonoarticulator awareness – CONFIART (SANTOS, VIEIRA and VIDOR-SOUZA, 2014) were also analyzed. For the auditory aspects of the LAEP, the variables were the measures of latency and amplitude of the right and left ears, as well as the qualitative description of the occurrence of the P300 wave. The main statistical method used as a criterion for estimating the effects in each therapy group was the linear regression model with mixed effects (FAUSTO et al., 2008; PINHEIRO et al., 2017) for the quantitative response variables. This model uses fixed effect for the therapy group and random effects for children in the treatment periods, extracting information from the data more accurately than the traditional linear models, which usually use only fixed effects for the explanatory

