variables. The main inferential utility of the linear regression model is related to the interpretation of the significant coefficients, with which it is possible to have an estimate for the change in the level of the phonological aspects considered in the research, among them: phonetic inventory, phonological system, distinctive features and phonological processes. The polytomic logistic model was also used for the variables of ordinal qualitative responses, which included the analysis of PCFO performance (SEABRA and CAPOVILLA, 2012) and the evaluation of phonoarticulatory awareness. (SANTOS, VIEIRA and VIDOR-SOUZA, 2014). The advantage of the application of logistic models is mainly the determination of the odds factor through the exponentiation of the estimated coefficients. Other tests involved in validating the results include Fisher's Exact, ShaphiroWilk and Levene T for correlated samples and Analysis of Variance. Chi-Square and Wilcoxon tests were applied to the PEALL variables. For all hypothesis tests, a significance level of 0.05 was set.

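### The main mixed model for before-and-after data names only therapy group as a fixed effect; fitted as worded, its group coefficient is not the therapy effect and carries only a fraction of it

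*Combined protocol and SAP*

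**What the plan says.** The Objectives section states that "The children were randomly drawn among three groups": Placebo, Cycles Traditional and SIFALA. It says the analysis was meant to "estimate the effects in each therapy group using the linear regression model with mixed effects for the quantitative variables responses".

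The Statistical Analysis Plan section says the chosen variables describe "phonological and auditory aspects of the evaluations applied before and after the treatment period", so there are two assessment times per child. It calls the mixed model the main method for quantitative responses and describes its terms in one sentence: "This model uses fixed effect for the therapy group and random effects for children in the treatment periods". It adds that from the significant coefficients "it is possible to have an estimate for the change in the level of the phonological aspects considered in the research".

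Other methods are listed without a stated response or contrast, among them "T for correlated samples and Analysis of Variance". For ordinal outcomes the section says: "The polytomic logistic model was also used for the variables of ordinal qualitative responses, which included the analysis of PCFO performance"; phonoarticulatory awareness (CONFIART) is handled the same way.

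The document gives no model equation, sample size, SD, pre/post correlation or target effect.

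**The concern.** In a randomised trial with a baseline and a post-treatment value, the therapy effect is a difference between groups in how the outcome moves, or a difference in the post-treatment value given baseline. A mixed model estimates it through a group-by-period term, a baseline covariate or a change-score response. The plan names none of these. Period is mentioned only in the random part, and a random effect does not supply a contrast between groups.

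With group alone in the fixed part, the group coefficient pools both assessment times, including the one taken before any treatment had been given. At stake are the size of the between-group estimates and the chance of detecting a real difference among the three groups. A reader also cannot tell which coefficient answers the trial's question.

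**Working it through.** The plan gives no figure to reproduce, so the check asks what the stated model estimates.

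**Inputs from the document.** Three randomised groups; two assessments per child; group as the only named fixed effect; random effects for children in the treatment periods; significance level 0.05.

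**Assumptions.** Complete pairs; two-sided tests (sidedness is not stated). Notation: *d* is the therapy effect in SD units, *r* the pre/post correlation, *k* the post/pre SD ratio, *n* the children per arm.

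**Step 1: what the coefficient is.** With group as the only fixed effect, generalised least squares gives

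group coefficient = w_pre × (baseline difference) + w_post × (post-treatment difference), with w_pre + w_post = 1.

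Randomisation makes the expected baseline difference zero, so the expected coefficient is w_post × *d*.

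**Step 2: the weight under two readings of the random part.**

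- *Random child intercept.* The two times have equal variance, so w_post = 0.5 whatever *n*, *r* or *d*. Mixed-model fits matched the between-group difference in (pre + post)/2 to within 3 × 10⁻¹³.
- *Child-specific period effect.* Pre and post variances may differ, and w_post = (1 − r·k) / (1 + k² − 2r·k). At an assumed r = 0.6:

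| k | calculation | w_post |
|---|---|---|
| 0.7 | 0.58 / 0.65 | 0.89 |
| 1.0 | 0.40 / 0.80 | 0.50 |
| 1.3 | 0.22 / 1.13 | 0.19 |

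Under either reading the coefficient is not the therapy effect. Only the first reading fixes the fraction at one half.

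**Step 3: power under the random-intercept reading (illustration only).** Assume n = 15 per arm and SD = 1 at both times. Noncentralities for a pairwise comparison:

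- group only: (d/2) / √[(1 + r)/n]
- group-by-period: d / √[4(1 − r)/n]
- baseline-adjusted: d / √[2(1 − r²)/n]

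For r = 0.7 and d = 1 these are 0.5/√(1.7/15) = 1.485, 1/√(1.2/15) = 3.536 and 1/√(1.02/15) = 3.835. The reference is a noncentral t with 3n − 3 = 42 df (41 for baseline-adjusted).

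| r | d | group only | group-by-period | baseline-adjusted |
|---|---|---|---|---|
| 0.7 | 1.0 | 31% | 93% | 96% |
| 0.5 | 0.5 | 12% | 27% | 34% |
| 0.5 | 0.3 | 7.5% | 12.6% | 15.3% |
| 0 | 0.3 | 8.8% | 8.8% | 12.6% |

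The large-sample multiple of children that the group-only model needs for equal power is (1 + r)/(1 − r) against group-by-period: 1.0, 3.0 and 5.7 at r = 0, 0.5 and 0.7. Against baseline adjustment it is 2/(1 − r): 2.0, 4.0 and 6.7.

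**Step 4: simulation.** With 20,000 data sets, a common gain of 0.5 SD, r = 0.7 and d = 1, the mean estimates were 0.500 (group only), 0.999 (group-by-period) and 0.999 (baseline-adjusted). With d = 0 the group-only test rejected in 5.1% (r = 0.7) and 4.9% (r = 0.5).

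**Step 5: a large shared gain.** With no period term, a gain common to all groups goes into the residual and can push the estimated child variance to zero. With a gain of 2 SD, type I error fell to about 3% (r = 0.7) and 2% (r = 0.5). Power at r = 0.7 and d = 1 fell from 31% to 18%. The test becomes conservative, not liberal.

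**The case against.** The strongest reply is that the sentence is not a full specification. It does not say group is the only fixed effect, and its purpose is to contrast mixed models with models that have fixed effects only. The aim of estimating effects in each therapy group, and the remark about change in level, suggest that a period contrast was intended. This stands as a reason for caution: an incomplete description is at least as plausible as a misfitted model. It does not close the gap, because the fixed terms and the coefficient carrying the treatment effect are still unstated. The remark about change may also be only a general comment on coefficients, and the point does not depend on it.

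A second reply is that the random part need not be a child intercept. That is right, and it rules out a flat claim of one half.

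A third is that the supporting tests cover the comparison. They do not as written. The correlated-samples test most naturally compares pre with post within a group, although the plan does not say so, and the Analysis of Variance has no stated response.

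A fourth is that the power figures say nothing specific about this trial. That also stands: the gap to group-by-period runs from none to 62 percentage points (93 − 31) depending on assumed inputs.

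A reader might infer three stronger things: that all reported between-group estimates are half the truth, that the wrong model was certainly fitted, or that false positives are inflated. The document supports none of them. The half needs a random child intercept and complete pairs, the fitted model is not shown, and under the random-intercept reading the test holds its level or is conservative.

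**Conclusion.** The concern holds as a defect in the stated model. Fitted as worded, the group coefficient does not estimate the therapy effect. In expectation it carries one half of it under a random child intercept with complete pairs. Under a child-specific period effect the fraction varies with the post/pre SD ratio, from about 0.9 to 0.2 for ratios of 0.7 to 1.3 at an assumed correlation of 0.6.

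Under the random-intercept reading there is no excess of false positives. The loss of power relative to a group-by-period test is nil at zero pre/post correlation and grows with the correlation; how much it matters in this trial cannot be computed from the document.

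Whether the results are affected depends on what was fitted, which is unknown. If period terms or change scores were used, the analysis may be sound and only the text needs correcting. It should be fixed; confidence is medium.

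The ordinal PCFO and CONFIART models have a separate, secondary reporting gap: the plan does not say how pre and post values enter. No calculation bears on that.

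**What to change.** State the model equation. Either of two forms would do:

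- fixed effects for group, period and group-by-period, with a child random effect, naming the three pairwise group-by-period contrasts (SIFALA vs Placebo, Cycles vs Placebo, SIFALA vs Cycles) as the treatment effects; or
- the post-treatment value modelled by group, with its own baseline value as covariate, and the same three pairwise contrasts.

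Say exactly what the random part contains. If period terms were already fitted, state them and name the coefficients that carry the treatment effect. If the literal model was fitted, re-run one of the two forms on the existing data.

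For PCFO and CONFIART, state how the two assessments enter: for example, the post-treatment category adjusted for the baseline category, or a cumulative-logit model with a child random intercept and the same fixed terms.

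The cost is a wording change and, only if the literal model was used, a re-analysis. No new data are needed.

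### The SAP names no baseline, period or group-by-period term, so the group effect is unclear and pre-treatment values already collected are not used as covariates

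*Combined protocol and SAP*

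**What the plan says.** The Objectives section of the combined protocol and SAP lists the phonological aspects under study as "phonetic inventory, phonological system, severity of the speech sound disorders, altered distinctive traits and phonological processes", and states that "Comparisons of the phonological and auditory aspects were performed before and after the intensive period of treatment". Before-treatment values of the outcomes, severity included, should therefore be on file. The scale of severity is not given. On allocation the section says "The children were randomly drawn among three groups"; no stratification or balancing is described.

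The Statistical Analysis Plan says its variables "characterize the phonological and auditory aspects of the evaluations applied before and after the treatment period". For quantitative responses it specifies a linear mixed model: "This model uses fixed effect for the therapy group", continuing "and random effects for children in the treatment periods". On what the coefficients mean, it says that with the significant ones "it is possible to have an estimate for the change in the level of the phonological aspects considered in the research". PCFO and CONFIART go to a polytomous logistic model for which no terms are listed. The auditory evoked potential (LAEP) variables go to Chi-Square and Wilcoxon tests. Sample size, power, effect size, standard deviations, before-after correlations and sidedness are not stated.

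**The concern.** The data are before-and-after pairs in three randomised arms, and the question is whether the arms improve by different amounts. A model answers that if it has a group-by-period term, or if it takes the after value as response and the before value as covariate. The SAP names neither. Therapy group is the only fixed effect mentioned, and a group main effect fitted to stacked before and after rows does not measure differential improvement.

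Two things are at stake. The first is meaning: a reader cannot tell whether a significant coefficient reflects change or an average level that includes the period before treatment. The second is efficiency: the before-treatment value of each outcome, usually its best single predictor, is in hand but not named as a covariate. The gap is widest for PCFO and CONFIART, where no child effect is named either, so nothing stated links a child's before and after scores.

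**Working it through.** The documents give no figure to reproduce. Everything below is illustration under assumptions: outcome SD 1 at both times, before-after correlation ρ from 0.3 to 0.9, complete pairs, treatment effect δ, and (for power) two-sided 0.05.

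**Variance of a two-arm contrast, relative to comparing after values only**

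- After-only: 1
- Before-after change (group-by-period with a random child intercept): 2(1 − ρ)
- Baseline-adjusted: 1 − ρ²
- Ratio of adjusted to change: (1 − ρ²) / [2(1 − ρ)] = (1 + ρ)/2

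| ρ | Change | Adjusted | Adjusted ÷ change | Adjusted ÷ after-only |
|---|---|---|---|---|
| 0.3 | 1.40 | 0.91 | 0.65 | 0.91 |
| 0.5 | 1.00 | 0.75 | 0.75 | 0.75 |
| 0.7 | 0.60 | 0.51 | 0.85 | 0.51 |
| 0.9 | 0.20 | 0.19 | 0.95 | 0.19 |

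The reduction against the change contrast is 35% / 25% / 15% / 5%. Against an after-only comparison it is 9% / 25% / 49% at ρ = 0.3 / 0.5 / 0.7, and it moves in the opposite direction as ρ rises.

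**Literal reading: group as the only fixed effect, with a random child intercept**

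The coefficient is the arm difference in each child's mean of before and after. It estimates δ/2 with relative variance (1 + ρ)/2.

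**Error in the contrast from a chance baseline difference of d = 0.5 SD**

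- Group only: d(1 + ρ)/2 = 0.375 / 0.425 / 0.475 SD at ρ = 0.5 / 0.7 / 0.9
- Change: d(ρ − 1) = −0.25 / −0.15 / −0.05 SD, which is regression to the mean
- Baseline-adjusted: 0

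The SD of a baseline difference between two arms is √(2/n). A difference beyond 0.5 SD between a given pair then has probability 26% with an assumed 10 children per arm and 11% with 20.

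**Power**, assuming 10 per arm, δ = 1 SD and ρ = 0.7, from Φ(effect / [SD·√(2/10)] − 1.96):

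- Group only: 0.5 / (√0.85 × 0.447) = 1.21, power 0.23
- Change: 1 / (√0.60 × 0.447) = 2.89, power 0.82
- Baseline-adjusted: 1 / (√0.51 × 0.447) = 3.13, power 0.88

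This normal approximation ignores the degree of freedom spent on the covariate.

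**What severity adds**

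In one simulated data set (3 × 10 children), the group-by-period estimate was 1.2264 (SE 0.3400) both with and without a severity main effect. Once the outcome's own baseline is in the model, severity's further variance reduction is its squared partial correlation, (r_ys − r_yb·r_bs)² / [(1 − r_yb²)(1 − r_bs²)], where y is the after value, b its baseline and s severity. With r_yb = 0.7 assumed:

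- r_ys = 0.5, r_bs = 0.5: 0.15² / (0.51 × 0.75) = 0.059, about 6%
- r_ys = 0.5, r_bs = 0.7: 0.01² / (0.51 × 0.51) = 0.0004, about 0%
- r_ys = 0.7, r_bs = 0.7: 0.21² / (0.51 × 0.51) = 0.170, about 17%

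**The case against.** The strongest reply is that the sentence on the fixed effect does not stop there. It adds random effects for children in the treatment periods, both evaluations enter the data, and the stated target is change. A reader might infer that the model holds nothing but therapy group and that imbalance in severity goes wholly uncorrected. The documents do not support that. If group-by-period was fitted with a child effect, stable differences between children, severity among them, largely cancel for the quantitative outcomes.

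This stands as a limit on the point but does not remove it. The group-by-period term has to be supplied by the reader, and random effects alone do not turn a group main effect into a contrast of change. Even with that term, the change contrast keeps the variance penalty and the regression-to-the-mean error shown above.

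Other replies also have force. An unadjusted randomised comparison is valid, and its standard error already allows for chance imbalance; the case for adjustment is precision and robustness, not repair of bias. Odds ratios are non-collapsible: in the ordinal models, adjustment can raise power and protects against chance imbalance, but it generally does not narrow the interval for the log odds ratio, and it changes the quantity estimated to a conditional one. The LAEP tests fall outside the proposal. Finally, the document already reports that most treated children improved, so covariates chosen now are chosen after results were seen.

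**Conclusion.** The point holds in a limited form. The SAP does not show how before-treatment values enter any model, and a better specification is available from data already collected.

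The size depends on which model was fitted. If group was the only fixed effect, the missing period and group-by-period terms are the larger defect: half the effect is estimated, and power is about 0.23 against 0.88 in the illustration. If a group-by-period contrast was fitted, the loss is modest, with baseline adjustment cutting variance by 35% to 5% as ρ goes from 0.3 to 0.9. For PCFO and CONFIART no baseline or child term is named, so the point applies there without that mitigation.

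A reader might infer that leaving out severity costs 9% to 49% of residual variance. That range assumes an after-only comparison, which the SAP does not describe, and treats severity as the sole baseline predictor. Most of the gain would come from each outcome's own baseline. All correlations, the effect size and the group sizes are assumptions.

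**What to change.** Write each model out in full.

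- **Quantitative outcomes:** after-treatment value ~ therapy group + before-treatment value of the same outcome. If the mixed model is kept alongside, state whether it contains period and group-by-period terms, and which coefficient is the treatment contrast.
- **PCFO and CONFIART:** add the before-treatment score of the same instrument to the ordinal model, and describe the odds ratio as conditional on it.
- **Severity:** before-treatment severity may be one further covariate where group size allows. Where severity is itself the outcome, its baseline is the only covariate.
- **LAEP tests:** unchanged by this proposal.

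The cost is SAP wording and a re-run on data already held. Each continuous covariate takes one degree of freedom; severity takes more if it is categorical. In small groups, extra terms in the ordinal models may create sparse cells, so the own-baseline score comes first and severity second. The re-analysis must be labelled post hoc and shown beside the results already reported.

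### Reading inference from model coefficients does not yield all three between-arm comparisons, and the SAP names no contrast, so a SIFALA versus Cycles test is not assured

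*Combined protocol and SAP*

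**What the plan says.** The Objectives section gives three arms: "The children were randomly drawn among three groups". It states an aim to analyse and compare, but describes the comparison in time: "Comparisons of the phonological and auditory aspects were performed before and after the intensive period of treatment in children with speech sound disorders". No pair of arms is named.

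The Statistical Analysis Plan sets the target and the terms of the main model:

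- Target: "The main statistical method used as a criterion for estimating the effects in each therapy group was the linear regression model with mixed effects".
- Terms: "This model uses fixed effect for the therapy group and random effects for children in the treatment periods". No fixed period term, group-by-period interaction, factor coding or reference arm is given.
- Inference, quantitative outcomes: "The main inferential utility of the linear regression model is related to the interpretation of the significant coefficients".
- Inference, ordinal outcomes: the stated advantage of the logistic model is "the determination of the odds factor through the exponentiation of the estimated coefficients".

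The SAP also lists Fisher's exact test, Shapiro-Wilk, Levene, a t test for correlated samples and analysis of variance as validating tests. Chi-Square and Wilcoxon tests are assigned to the evoked-potential variables. The level is 0.05 throughout, with no multiplicity rule. The summary that closes the Objectives section says of the therapies that it is "being possible to point out as innovative and differentiated the model using" the software.

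**The concern.** Three arms make three pairwise questions: SIFALA against Placebo, Cycles against Placebo, and SIFALA against Cycles. The third is the only randomised comparison of the software therapy with the traditional one. A plan that draws its conclusions from individual coefficients answers only those questions that happen to be coefficients, and which ones those are depends on a coding choice that the SAP does not record.

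If the SIFALA-Cycles comparison has no coefficient, a reader is left to set two coefficients side by side and note which is significant. That is not a test of their difference, and it can suggest a difference between two equally effective therapies. The emphasis on significant coefficients, together with a summary that singles out the software model, makes that shortcut easy to take.

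**Working it through.** The documents give no sample size, power, effect size or standard deviation, so there is no planned figure to reproduce. The check is structural, followed by an illustration on stated assumptions.

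**1. What one fit delivers under each reading of the SAP**

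| Reading of the coefficients | Group coefficients | Pairwise differences read directly |
|---|---|---|
| Reference coding, Placebo as reference | 2 | SIFALA-Placebo, Cycles-Placebo |
| Reference coding, Cycles as reference | 2 | SIFALA-Cycles, Placebo-Cycles |
| Reference coding, SIFALA as reference | 2 | Placebo-SIFALA, Cycles-SIFALA |
| One mean per arm (cell-means coding) | 3 | none |
| One pre-to-post change per arm | 3 | none |

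No row gives all three pairs.

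**2. Whether the other listed tests fill the gap**

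- Analysis of variance: its factor is not stated. Across arms it would be an omnibus test, which does not say which pair differs.
- t test for correlated samples: compares a child with itself.
- Shapiro-Wilk and Levene: check assumptions.
- Fisher's exact, Chi-Square and Wilcoxon: no pair of arms is named, and the last two are for the evoked-potential variables.

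**3. Whether the contrast can be recovered**

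I simulated pre/post data for three arms (12 children per arm, assumed) and fitted a mixed model with group, period and their interaction. With Placebo as reference, the interaction coefficients were 7.471 (SIFALA) and 4.196 (Cycles). Their difference, from unrounded values, was 3.276 with SE 1.424. Refitting with Cycles as reference gave SIFALA as a direct coefficient of 3.276, SE 1.424. The two agree, so the comparison is estimable from the same fit.

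**4. Illustration: inferring a difference when exactly one coefficient is significant**

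Assumptions: equal arms, equal known variance σ², the same true effect for both therapies, Placebo as reference, two-sided 0.05.

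- Correlation of the two coefficients: each has variance 2σ²/n, and their covariance is the Placebo variance σ²/n, so the correlation is (σ²/n)/(2σ²/n) = 0.5.
- Mean of each z-statistic for power p: 1.96 + Φ⁻¹(p).
- P(exactly one significant) = 2 × [p − P(both significant)].

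| Power of each coefficient | P(both) | P(exactly one) |
|---|---|---|
| 20% | 0.087 | 0.226 |
| 30% | 0.157 | 0.286 |
| 50% | 0.333 | 0.333 |
| 70% | 0.557 | 0.286 |
| 80% | 0.687 | 0.226 |
| 90% | 0.832 | 0.135 |

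For example, at 50% power: 2 × (0.5 − 0.333) = 0.333. A direct SIFALA-Cycles test has mean zero here and errs 5% of the time.

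**5. Cost of testing all three pairs unadjusted**

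Under no difference between any arms, with equal arms and known variance, the chance of at least one false positive is about 12%. If the tests were independent it would be 1 − 0.95³ = 0.143.

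**The case against.** A reader might infer that SIFALA versus Cycles is never estimated or tested. The documents do not support that. They state neither the coding nor the reference arm, nor do they say that any pair is left out. With Cycles as reference the comparison would be a coefficient, and under any coding it is a linear combination of what is fitted. The sentence about significant coefficients explains why the model is useful; it does not confine reporting to one parameterisation. All of this stands.

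The coefficients may also be meant as changes within each arm, since the SAP speaks of effects in each group and of comparisons before and after treatment. That is a fair reading, but it leaves no between-arm difference among the coefficients. It also exposes a more basic gap: the only fixed effect described is therapy group. With pre and post data, contrasts of that term would compare levels averaged over both occasions, not changes. Asking only for contrasts from the model as written would therefore not be enough.

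The percentages above rest on a decision rule that the SAP does not state, and on assumed power and allocation. They show a risk, not an error that was made. Finally, the closing summary credits the therapeutic models in the plural and claims no superiority for SIFALA. Calling it differentiated may refer only to its format, so that sentence is weak evidence of a comparative claim.

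**Conclusion.** The point holds as a gap in the stated procedure. The SAP names no reference arm, contrast or post-hoc test, and coefficients from a single fit do not give all three between-arm comparisons under any of the readings considered. The structural conclusion rests only on there being three arms and on inference being read from coefficients.

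It does not follow that the SIFALA-Cycles comparison was omitted; the analysts may have computed it. The size is illustrative: about 14% to 33% false inference of a difference, against 5% for a direct test, if a reader relied on exactly one coefficient being significant. That assumes equally effective therapies, equal arms, a shared Placebo reference and 20% to 90% power per coefficient. The plan should be changed, because a trial that aims to compare three randomised arms ought to guarantee each comparison it may be read as making, and the remedy is cheap.

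**What to change.** Amend the Statistical Analysis Plan as follows.

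1. Add fixed terms for period and group-by-period to the models, and state the coding and reference arm.
2. For each outcome, compute three between-arm differences in pre-to-post change as contrasts: SIFALA-Placebo, Cycles-Placebo and SIFALA-Cycles. Report each with its standard error, 95% interval and p-value. For the ordinal outcomes, exponentiate the contrasts to the odds-ratio scale; with pre and post in one model these are ratios of odds ratios.
3. Control multiplicity over the three contrasts, for example by testing them only after a significant omnibus group-by-period test, or with a Holm adjustment, where the smallest p-value is compared with 0.05/3 = 0.0167.
4. State that any claim that SIFALA differs from Cycles rests only on the SIFALA-Cycles contrast.

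The cost is revised wording, two further model terms, a contrast statement per model and somewhat stricter p-values. No new data are needed.

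### A within-arm paired t test is listed among the tests that validate the results, although it makes no comparison with Placebo and can be significant through natural improvement alone

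*Combined protocol and SAP*

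**What the plan says.** The design has three randomised arms: "The children were randomly drawn among three groups". One is a Placebo arm: "This group received no specific treatment for speech deviations, only used the computer resource to play on a website". Measurements are taken at two times, before and after treatment.

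For quantitative responses, the Statistical Analysis Plan assigns the inference to a mixed model: "The main statistical method used as a criterion for estimating the effects in each therapy group was the linear regression model with mixed effects". It describes that model as having a fixed term for therapy group and random terms for the children across periods. It names no group-by-period term and no baseline covariate.

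Near its end, the plan adds a second set of tests: "Other tests involved in validating the results include" Fisher's exact test, then "ShaphiroWilk and Levene T for correlated samples and Analysis of Variance". The punctuation is broken. I read it as Fisher's exact test, Shapiro-Wilk, Levene, a t test for correlated samples (a paired t test) and Analysis of Variance. The plan does not say which variable, arm or comparison each test uses. It then sets one level for all of them: "For all hypothesis tests, a significance level of 0.05 was set".

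**The concern.** Shapiro-Wilk and Levene check model conditions. A paired t test does not: it tests an effect, namely whether the mean change in one group of children differs from zero. Children with speech sound disorders may improve over a treatment period because they mature or because they have met the test before. The Placebo arm exists to separate such gains from the effect of therapy. A paired t test within a therapy arm discards that information, yet the plan lists it among the tests that support its results.

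It is also computed on the same before and after evaluations as the mixed model, so agreement between the two is not independent evidence. What is at stake is false reassurance: a therapy no better than Placebo could be reported as supported by a significant paired test.

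**Working it through.** **Inputs from the documents.** Three arms including Placebo; two measurement times; level 0.05. The plan states no operating characteristic, so there is no figure of its own to reproduce.

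**Assumed inputs.** Two-sided tests, complete data, SD 1 at both times, equal arms of 10 or 15 children, before/after correlation r of 0.5 to 0.7, and a natural gain g of 0.5 SD or 0.2 SD in every arm. The therapy effect over Placebo is zero.

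**Step 1: paired t test in one therapy arm.** The SD of the change is √(2(1−r)), so the noncentrality is g√n / √(2(1−r)). The probability of significance comes from the noncentral t distribution with n−1 degrees of freedom. The critical value is 2.262 at n = 10 and 2.145 at n = 15.

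| n per arm | g (SD) | r | Noncentrality | P(significant) |
|---|---|---|---|---|
| 10 | 0.5 | 0.5 | 0.5 × √10 / √1.0 = 1.58 | 0.29 |
| 10 | 0.5 | 0.7 | 0.5 × √10 / √0.6 = 2.04 | 0.45 |
| 15 | 0.5 | 0.5 | 0.5 × √15 / √1.0 = 1.94 | 0.44 |
| 15 | 0.5 | 0.7 | 0.5 × √15 / √0.6 = 2.50 | 0.64 |
| 10 | 0.2 | 0.5 | 0.2 × √10 / √1.0 = 0.63 | 0.09 |
| 10 | 0.2 | 0.7 | 0.2 × √10 / √0.6 = 0.82 | 0.11 |

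The nominal rate is 0.05, and it applies only if g = 0. Any non-zero natural gain raises the rate, and more children or a higher correlation raise it further. At g = 0.5 and 20 per arm it is 0.56 to 0.78 over the same correlations.

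**Step 2: Analysis of Variance.** The documents do not say what enters it, so both readings were checked. Suppose both therapies are truly d = 0.8 SD better than Placebo. The arm means are then (0, d, d), and the noncentral F parameter is n × (2/3)d² / v, where v is the residual variance: 1 for after-values, 2(1−r) for change, and 1−r² with baseline as a covariate. For after-values at n = 10 this is 10 × (2/3) × 0.64 / 1 = 4.27. Power at 10 per arm:

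| r | After-values | Change | Baseline as covariate |
|---|---|---|---|
| 0.3 | 0.40 | 0.30 | 0.43 |
| 0.5 | 0.40 | 0.40 | 0.51 |
| 0.7 | 0.40 | 0.61 | 0.68 |

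With two time points and complete data, an ANOVA of change is the same test as the group-by-period term of a random-intercept mixed model. It would therefore have no loss of power against that model.

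**The case against.** The strongest defence is that the mixed model is named as the main method, so the other tests are only supportive. Because the same sentence lists Shapiro-Wilk and Levene, validation may partly mean checking model conditions. This stands in part: nothing in the plan makes a result stand or fall by agreement with the paired t test. It does not rescue the test, because a paired t test checks no model condition, and offering it as support for a therapy effect is wrong even in a secondary role.

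It is also fair to object that every magnitude above is assumed. The 0.5 SD gain drives the larger figures; at 0.2 SD the excess over 5% is modest. The direction does not depend on the choice, provided that some natural gain exists.

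A reader might go further and infer that the ANOVA often fails to confirm real effects. The documents do not support this. They never say that after-treatment values are analysed, and an ANOVA of change would not have the fault. Even for after-values, the shortfall depends on the comparison: at a correlation of 0.3 they have more power than change (0.40 against 0.30), and at 0.5 the two are equal. The wider gap at 0.7 against a baseline-adjusted analysis (0.40 against 0.68) uses a model that the plan does not name. With 30 per arm, after-value power at d = 0.8 is already 0.89.

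A reader might also infer that a true effect would be declared not validated, or that the lack of a rule for disagreement lets conclusions move either way. That too is inference. The plan states no such consequence and names its main method.

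**Conclusion.** The point holds for the paired t test. Used before and after treatment within a therapy arm, it cannot validate a therapy effect in a trial with a randomised Placebo arm. With no therapy effect, it is significant in 29-45% of cases at 10 per arm and 44-64% at 15 per arm for a natural gain of 0.5 SD and a correlation of 0.5 to 0.7, and in 9-11% at 10 per arm for a gain of 0.2 SD. Arm size, gain and correlation are assumptions, as is the reading that the test is applied within arms.

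For the Analysis of Variance, only a conditional statement is justified: if it uses unadjusted after-values, it could have less power than a contrast that uses baseline. Otherwise the finding is only that its input is unspecified.

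**What to change.** In the Statistical Analysis Plan:

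1. Remove the t test for correlated samples from the validating tests. Report within-arm change descriptively, without a p-value.
2. State that each quantitative phonological outcome is judged on the between-arm contrast in change. Name the term: either group-by-period in the mixed model, or group with baseline as a covariate. This must be written out because the model description currently names neither.
3. If an ANOVA is kept as a supportive check, apply it to the same between-arm contrast with baseline used, and say so.

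The change is to wording and reporting only; it needs no new data and no change of design. The sponsor gives up the within-arm p-values.
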